#### Study visit 2; wk 8 (Duration ~20 min)

In addition to the general chemistry panel, the blood draw will be used to assess carotenoids to reflect F&V intake (only if the participant is not currently taking vitamin A supplements).

At this study visit, they will be informed of their randomization into 1 of 3 discount level groups, stratified by gender within each grocery store. Subjects will receive, in paper, if they wish, and e-mail format, a summary of foods and beverages available for discount during the study as well as a list of conditions to remain in the study. Subjects will be asked to save their receipts if they believe they did not receive the expected discount, to bring to our attention (rather than to store staff or managers) at their next visit for possible reimbursement.

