Multi-level Supermarket Discounts of Fruits and Vegetables' Impact on Intake and Health
PI: [name]
NCT04178824
Document Date: 8-1-2023

Statistical Analysis Plan

Linear mixed effects modeling was performed to evaluate the group-by-time interaction of all outcomes from the intent-to-treat (ITT) sample, as a primary analysis, and the per-protocol sample, as a secondary analysis. The ITT sample was comprised of participants with at least one post-randomization measurement. The per-protocol sample was comprised of all participants who completed the study. Primary outcome measures were grams (g) of fruit, vegetable, non-caloric beverage intake, and body weight (expressed in kilograms (kg)). Secondary dietary outcomes were high-ED food intake (g), total fat intake (g), and daily energy intake (kcal). Secondary clinical outcomes were BMI (kg/m²), percent body fat, waist circumference (cm), metabolic risk factors (fasting glucose (mg/dL), cholesterol (mg/dL), and blood pressure (mmHg). The linear mixed model included the group-by-time interaction term, where time was the within-subjects factor and group was the between-subjects factor (fixed effects), and the participant as the random effect to obtain the within-person differences in response to the intervention. No covariates were added to the main model because there were no baseline differences in covariates between discount groups and the RCT study design reduces between-group differences (29). First, an omnibus test was performed to test the overall effect of the group-by-time on interaction on the outcome variables. Then, a planned comparison approach using difference-in-difference contrast (DiD) was done to evaluate the differential change in primary outcome variables. The main comparison of interest was the change between groups between the baseline and the first 16 weeks of the intervention (the mid-point of the intervention period), 32 weeks of the intervention (the end of the intervention period), and 16 weeks post-intervention (the end of the follow-up period). A sensitivity analysis was also performed on the ITT sample by adding key covariates to the model: sex, age at enrollment, season at enrollment, primary supermarket, COVID presence, and income level. The presence of COVID was assigned if the COVID-19 pandemic and lockdown period occurred during the intervention between 2/20/20 and 4/6/2021. The absence of COVID-19 was assigned if the COVID-19 pandemic period happened prior to or after the intervention. Income level was a dichotomous variable: above or below the median income in NYC. Estimated means and 95% confidence intervals are shown in tables and figures. Missing data was assumed to be missing at random (MAR). Two-tailed $P < .05$ was considered statistically significant. RStudio (RStudio version 2023.12.0 Build 369) was used to analyze all data.

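### The main model omits the randomisation strata (gender within store) for a reason that does not justify it; if change differs by sex or store, the primary standard errors are modestly too large

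*SAP*

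**What the plan says.** Protocol section 5f, under Study Visit 2 (week 8), has participants randomised to one of three discount levels, "stratified by gender within each grocery store".

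The SAP's main linear mixed model has group, time and their interaction as fixed effects, "and the participant as the random effect to obtain the within-person differences in response to the intervention". It has no sex or store term. Two reasons are given in one sentence. The first is "No covariates were added to the main model because there were no baseline differences in covariates between discount groups"; the second continues "and the RCT study design reduces between-group differences".

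For the primary outcomes, after an omnibus test, "a planned comparison approach using difference-in-difference contrast (DiD) was done to evaluate the differential change in primary outcome variables". The time points compared with baseline are 16 and 32 weeks of intervention and 16 weeks after it.

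A sensitivity analysis on the ITT sample is described as "adding key covariates to the model: sex, age at enrollment, season at enrollment, primary supermarket, COVID presence, and income level". Both stratification factors are in that list. No covariate-by-time terms are mentioned.

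**The concern.** Stratified allocation balances the arms on sex and store. Any part of the change over time that differs between strata is therefore largely removed from the real sampling error of the arm contrast. A model without those terms leaves that part in the residual and reports a standard error that is larger than it need be. This is why stratification factors normally go into the analysis by rule, without looking at the data.

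The SAP's first reason does not answer this. Balance on sex and store is what the allocation was built to produce, so observing it says nothing about whether those factors predict the outcome. The second reason explains why an unadjusted estimate is unbiased, but it leaves precision untouched.

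The sensitivity model looks like a remedy, but as worded it adds main effects only. What matters for a change contrast is whether sex or store alters the change, which needs sex-by-time and store-by-time terms. At stake is some precision in the primary intervals, and a stated rationale that would not survive a referee's question.

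**Working it through.** **Scale.** Protocol section 5c: 360 × (1 − 0.375) = 225 completers, which reproduces, or 75 per arm. (Section 5a gives 240 completers at 20% dropout, but 360 × 0.80 = 288; I use 225.) The documents give no SD, standard error or stratum effect, so everything below is in units of the residual SD σ and the stratum effects are assumptions.

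**Step 1: main effects cancel.** Write the outcome as fixed effects + β·(stratum) + participant effect + error. Then Y(t) − Y(baseline) contains neither β nor the participant effect. With complete data the contrast between two arms has SE = √(2σ² × 2/75) = 0.231σ, with or without β. Simulated data sets agree (225 completers, assumed four stores and 75% women, large stratum effects on level only, six data sets per scenario). The mean SE was 0.2345 for the SAP model and 0.2345 with sex and store added, and the estimates agreed to about 10⁻¹⁴. With 360 enrolled and 37.5% dropout the SEs were 0.2065 and 0.2047, and the largest difference in any one data set was 1.3%.

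**Step 2: strata that predict change.** Assume a random intercept, independent residuals, baseline plus three visits, balanced strata, and a stratum effect on change that is constant after baseline, with variance τ².

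- Share of the variance of change explained: R² = τ²/(τ² + 2σ²), so τ² = 2σ²R²/(1 − R²).
- The stratum profile over visits is (0, 1, 1, 1). Its centred sum of squares is 0.75² + 3 × 0.25² = 0.75. Spread over 3 within-person degrees of freedom, this adds 0.25τ² to the pooled residual variance.
- Reported SE ÷ actual SE = √(1 + 0.25τ²/σ²) = √(1 + 0.5R²/(1 − R²)).
- Actual two-sided size = 2[1 − Φ(1.96 × ratio)].

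| R² (assumed) | 0.5R²/(1 − R²) | SE ratio | SE too large by | Size of nominal 5% test |
|---|---|---|---|---|
| 3% | 0.0155 | 1.008 | 0.8% | 4.8% |
| 5% | 0.0263 | 1.013 | 1.3% | 4.7% |
| 10% | 0.0556 | 1.027 | 2.7% | 4.4% |
| 15% | 0.0882 | 1.043 | 4.3% | 4.1% |

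If the stratum effect instead grows linearly to the last visit, the profile is (0, 1/3, 2/3, 1), with centred sum of squares 0.556 and 0.185τ² added. At the last visit the SE is then 0.6, 1.0, 2.0 and 3.2% too large, and the size is 4.9, 4.8, 4.6 and 4.3%.

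**Step 3: check by simulation.** A strong case was simulated, with 1.0σ between the sexes and 1.0σ between the extreme stores in change. Here τ²/σ² = 0.75 × 0.25 + 0.139 = 0.326, so R² = 0.326/2.326 = 14%, and the formula gives √(1 + 0.25 × 0.326) = 1.040.

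- Complete data: SAP model 0.2432, with main effects 0.2432, with time interactions 0.2331. The ratio is 0.2432/0.2331 = 1.043.
- With 37.5% dropout: 0.2118, 0.2096 and 0.1998. The ratio of first to last is 1.060, of which about 1% comes from main effects because cancellation is then incomplete.
- Type I error of the SAP model, 1,500 complete-data trials each: 5.1% with no stratum effect on change, 5.0% with effects half as large as the strong case, and 4.3% in the strong case. The Monte Carlo SE is about 0.6 points, so the 4.3% alone is not conclusive.

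**The case against.** The strongest reply is that the primary contrast is a within-person change, so fixed differences between sexes and stores are already removed. Any remaining error is conservative, and nothing in the documents shows that sex or store predicts change. All of that stands. It makes this a precision point and not a validity point.

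A reader might go further and infer that the primary standard errors do not match the design, full stop. The documents do not support that: a mismatch needs stratum effects on change, for which there is no figure. A reader might also size the loss with 1/√(1 − R²), which gives 1.5, 2.6, 5.4 and 8.5% at the same R² values. That formula fits a change score from two time points. With a participant effect over four visits, the stratum signal is diluted in the pooled residual, and the loss is about half as large.

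A reader might infer too that the covariates were chosen after seeing the arms. The past tense and the appeal to observed balance invite that reading, but the SAP does not say when the decision was made. The weakness shown is the absence of a rule fixed in advance.

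Three further replies have force. The sentence about baseline differences covers covariates generally, not only the strata. Exact balance holds at randomisation and only approximately in an ITT sample that requires a post-randomisation measurement. And because the SAP reports its analysis as done, silently swapping the primary model now would itself be a change after the results. The fix has to respect that last point.

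**Conclusion.** The point holds in a limited form. The main model leaves out the two factors the trial randomises by, neither stated reason justifies this, and the sensitivity model as worded hardly tests the contrast that matters. The cost is conditional: about 1 to 4% excess in the standard error for R² between 3 and 15%, with a nominal 5% test running at about 4.8 to 4.1%, and essentially no cost if sex and store do not predict change. These figures rest on assumed R² values, a random intercept with independent residuals, four time points, balanced strata and a stratum effect constant after baseline. There is no bias in the estimate and no inflation of false positives. It is worth correcting because the correction is cheap and the present rationale is unsound.

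**What to change.** 1. Replace the baseline-balance sentence with a design-based rule: factors used to stratify randomisation are included in the model for every outcome, whatever balance is observed.
2. Fit the model with sex, store, sex-by-time and store-by-time. Pool very small stores by a rule that uses store size only.
3. Report it beside the unadjusted model. If results are already known, label it as a design-based correction so that both remain visible and neither is presented as the sole prior choice.
4. At the least, add the sex-by-time and store-by-time terms to the existing sensitivity model.

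The cost is SAP wording, a re-run and extra parameters. With four stores and four time points (both assumed), there is 1 sex term plus 3 store terms, each at 4 time points, or 16 parameters per outcome. That is small against about 225 completers. This additive form does not reproduce the sex-by-store cells exactly. Full cells would need 7 × 4 = 28 parameters on the same assumptions, and the choice should be stated.

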#### Study Visit 1; wk 0 (Duration: ~20 min)

After the results of the blood tests are reviewed, eligible subjects will be asked to come in for study visit 1. Prior to this visit, subjects will fast overnight for a minimum of 12 hours. Body temperature will be taken and a short Morning Questionnaire completed. Participants will also complete a Behavioral checklist (Appendix D), a F&V Liking assessment (Appendix F) as well as an Income questionnaire (Appendix B), either in-person or virtually using REDCap and a secure Zoom interface,. A small blood sample will be drawn and a general blood chemistry panel will be ordered (fasting glucose, protein bound glucose (fructosamine), lipid profile (total cholesterol, LDL, HDL, triglycerides) and CRP). Next, blood pressure readings will be made in duplicate.

Body weight will be assessed on a beam scale and body composition assessed using a Tanita scale based on bioelectrical impedance (BIA).

Subjects will then be instructed on how to complete 24-hour dietary recalls and estimate portion sizes and will complete a Brief Block FFQ on-site as well as a 7 day physical activity recall. At the close of visit 1, subjects will receive an individualized timetable for future study visits, and will agree to receive phone calls for 24-h dietary recalls (3 unannounced phone calls during 1 week in between study visits) and one physical activity recall without being given an exact date.

	Protocol Name:	Multi-level supermarket discounts of fruits and vegetables on intake and health
	Principal Investigator:	[name]
	Primary Contact Name/Contact Info:	[name] [contact] [name] [contact]
	Date Revised:	8/7/20
	Study Number:	HS#: 16-00407 GCO#: 16-1050

Subjects will be informed that there will be different discount levels (30, 15, 0%), and that those in the 0% discount group will receive a discount of 30% for 16 weeks after the study, beginning Week 57. The Allegiance-affiliated supermarket reward scan cards provided at visit 1 will be used to track purchases and to activate the discounts during the intervention period.

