#### Study Visit 2-5; wk 8, 24, 40, 56 (Duration: ~30 min)

These visits will take place at the hospital or Quest Diagnostics during the final week of each period end-point (wk 8, 24, 40 and 56).

Each one of these visits will be preceded by a 12-hour overnight fast. After completing the morning questionnaire, the nurse will take body temperature, blood pressure readings and draw a blood sample. The same chemistry panel described for visit 1 will be ordered. Body weight and body composition will be assessed as described for visit 1 and a Brief Block FFQ will be completed either in-person or virtually using REDCap and a secure Zoom interface,

Subjects will receive, in paper if they wish, and e-mail format, a summary of foods and beverages available for discount during the study as well as a list of conditions to remain in the study. At each visit, subjects will be asked to present the Allegiance affiliate supermarket tag provided to them for use in the study. Staff will confirm that the number on the tag presented matches the tag number provided at Visit 1.

Finally, subjects will be reminded that in the weeks following these visits they will receive phone calls for 24-h dietary and physical activity recalls, without being given exact dates.

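### The SAP does not say which visit is the baseline, although blood pressure, glucose and lipids are read twice before any discount; using only one reading forgoes up to a quarter of the contrast variance

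*SAP*

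**What the plan says.** The SAP fits a linear mixed model with a group-by-time interaction, "and the participant as the random effect to obtain the within-person differences in response to the intervention". It adds no adjustment: "No covariates were added to the main model". An omnibus interaction test comes first. Then a "difference-in-difference contrast (DiD) was done to evaluate the differential change in primary outcome variables", and the main comparison is described as "the change between groups between the baseline and the first 16 weeks of the intervention", with matching comparisons at the end of the intervention and at the end of follow-up. The baseline is not tied to a visit.

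The clinical measures are lower in rank: "Secondary clinical outcomes were BMI (kg/m²), percent body fat, waist circumference (cm), metabolic risk factors", the last group comprising glucose, cholesterol and blood pressure. The test level is given as "Two-tailed $P < .05$ was considered statistically significant".

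The protocol has two clinic visits before any discount:

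- **Week 0** (section 5f, Study Visit 1): a fasting chemistry panel with glucose and lipids, weight and bioimpedance, and blood pressure ("Next, blood pressure readings will be made in duplicate").
- **Week 8** (Study Visit 2-5): weight, body composition and blood pressure again, and for the blood tests "The same chemistry panel described for visit 1 will be ordered".

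The Brief Summary says that no discount runs during the baseline period. Participants learn their group at the week 8 visit.

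**The concern.** Two untreated readings of the same quantity exist, and the SAP does not say what happens to them. There are three broad possibilities, with different consequences.

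- One visit is the reference and the other does not enter the contrast. Information already collected is then lost on noisy outcomes.
- Both visits are separate time levels with free group effects. Part of the omnibus test then looks for a group difference in change between weeks 0 and 8, where the discount cannot have acted.
- Both are pooled as the pre-discount reference, which avoids both costs.

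An undefined reference also leaves room to choose it after seeing results. That applies to body weight too, a primary outcome in the SAP that is measured at both visits.

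**Working it through.** **The plan's own figure.** The documents give no SD, effect size, within-person correlation or power for these outcomes, so there is no contrast variance to reproduce. The nearest size figure is in Protocol section 5c: 360 × (1 − 0.375) = 225 completers, which reproduces. Equal allocation is an assumption (no ratio is stated) and gives 225/3 = 75 per arm. Section 5a gives 240 completers instead, but the variance ratios below do not depend on the number.

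**Inputs.** Visits at weeks 0, 8, 24, 40 and 56 (Protocol 5f). Participant random effect, read as a random intercept; no covariates; two-sided 0.05 (SAP). Let σ² be the residual within-person variance.

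**Step 1: contrast variance under the SAP's model.** The random intercept cancels in a change score.

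- Change from one visit: σ² + σ² = 2.0σ².
- Change from the mean of weeks 0 and 8: σ² + σ²/2 = 1.5σ².
- Ratio 1.5/2.0 = 0.75, so 25% less variance; √0.75 = 0.866, so a standard error 13.4% smaller.

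In terms of correlation ρ, with total variance 1, these are 2(1 − ρ) and 1 + (1 + ρ)/2 − 2ρ = 1.5(1 − ρ). The ratio is therefore the same for every ρ and for weeks 24, 40 and 56. A fitted random-intercept model gave 0.750, and 20,000 simulated trials gave 0.748.

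Illustration with 75 per arm: the difference with 80% power from one reading is (1.960 + 0.842) × √(2 × 2.0/75) σ = 0.647σ. With two readings the standard error is √(2 × 1.5/75) σ = 0.200σ, and 0.647/0.200 − 1.960 = 1.275, which is 89.9% power. Equivalently, 75 × 0.75 = 56.25, so 57 per arm would do.

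**Step 2: other correlation patterns (assumed, since the documents give none).** Variance saved by the mean of weeks 0 and 8, over the three later visits:

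| Pattern | Against week 8 | Against week 0 |
|---|---|---|
| Equal correlation, ρ 0.3 to 0.9 | 25% | 25% |
| Random intercept 0.5 + AR(1) 0.3 + noise 0.2, 8-week AR correlation 0.9 | 14.5% to 17.6% | 18.4% to 24.8% |
| Random intercept 0.3 + AR(1) 0.5 + noise 0.2, 8-week AR correlation 0.9 | 11.3% to 14.3% | 16.4% to 24.7% |
| Pure AR(1), 8-week correlation 0.80 to 0.98 | −11.6% to +3.2% | 9.6% to 24.8% |

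**Step 3: the omnibus test.** Three groups and four time levels give 2 × 3 = 6 df; five time levels give 2 × 4 = 8 df. A noncentrality of 13.62 gives 80.0% power on 6 df and 75.1% on 8 df.

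Noncentrality also depends on how many pre-discount readings are in the model. For an effect constant over weeks 24, 40 and 56, under a random intercept, it is proportional to 3 × 1/4 = 0.75 with one pre-discount visit and to 3 × 2/5 = 1.20 with two. Setting the pooled design to 80%:

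| Coding | Noncentrality | df | Power |
|---|---|---|---|
| Both readings, one pre-discount level | 13.62 | 6 | 80% |
| Both readings, free levels | 13.62 | 8 | 75% |
| One reading only | 13.62 × 0.75/1.20 = 8.52 | 6 | 56% |

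The 56% depends on the effect pattern. It becomes 61% if half the effect remains at week 56, and 71% if none does.

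**The case against.** **The SAP may not use a single visit.** A reader might infer from the wording that one reading is discarded. The documents do not support that: the visit is not named, and the protocol uses baseline for an eight-week period, so a pooled reference is a possible reading. What stands is that the reference is undefined.

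**The contrast is described for primary outcomes.** This is right and limits the reach. Dietary recalls are taken once per period, in its middle (Protocol, Measures), so recalled fruit, vegetable and beverage intake has one pre-discount set and nothing to average. The study was powered on fruit and vegetable intake. Blood pressure, glucose and lipids are secondary, and the SAP explicitly assigns them only the group-by-time model. The coding of the baseline affects that test as well.

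**A quarter is not a general figure.** Also right. It needs equal correlation between all visits. Where correlation decays with no added noise, plain averaging can lose precision against week 8. That is a reason not to average quantities that drift, such as body weight and BMI, or percent body fat, which comes from the bioimpedance assessment made alongside weight.

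**Week 8 alone is defensible.** Week 0 precedes the move to doing all grocery shopping at one store. That shift is common to all arms and occurs before allocation is disclosed, so including week 0 does not bias the comparison. Using week 8 alone does not bias it either; the choice is one of precision.

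**The 8-df figure is easily misread.** The step from 80% to 75% compares two ways of coding the same two readings. It is not a loss relative to a single-visit baseline. If the single-visit test has 80% power, adding the second visit even as a free level raises noncentrality by 1.20/0.75 = 1.6 and power to about 94%, given a constant effect.

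**Conclusion.** The point holds as a gap in definition with a moderate precision cost for secondary outcomes. The SAP should say what its baseline is. If one visit is used for blood pressure, glucose or lipids, 25% of the contrast variance is carried unnecessarily under the SAP's own random-intercept model. Against week 8 the figure is about 11-18% with partly decaying correlation plus noise, and it is nil or negative under pure AR(1). If both visits are free levels, the omnibus test spends 2 of 8 df where no effect can exist, worth about 5 percentage points at the same noncentrality.

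A reader might go further and infer that the treatment comparison is biased or that the intake result is weakened. Neither follows: each choice of baseline gives a valid randomised contrast, and intake has one pre-discount recall set. The sizes rest on the assumed correlation patterns; the power figures also rest on the assumed effect patterns and, for the 75-per-arm illustration, on equal allocation.

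**What to change.** Define the baseline in the SAP for each outcome.

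- **Blood pressure, fasting glucose, lipids:** use both week 0 and week 8 as the pre-discount reference. Either take their mean, or keep both visits in the model with their own time effects and group means constrained equal before the discount. Use the same coding in the omnibus test.
- **Body weight, BMI, percent body fat:** name week 8 as the reference in both the contrasts and the omnibus test.
- **Recalled intake:** no change; state that the single pre-discount recall set is the baseline.

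No new data are needed. The cost is a few lines of SAP text and some re-analysis. The week 0 reading also comes from before the switch to single-store shopping, which should be acknowledged. The SAP is written in the past tense, so the results may already be known. In that case the sponsor should report which visit was used and present the two-reading analysis as a labelled sensitivity analysis, not as a replacement.

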**24-h Dietary Recalls (NDSR):** The 24-hour dietary recalls will be collected using Nutrition Data System for Research (NDSR), a computer-based software application developed at the University of Minnesota Nutrition Coordinating Center (NCC) that facilitates the collection of recalls in a standardized fashion. After all foods are coded and assigned weights, they will be reviewed, edited, and analyzed using the NDSR, which encompasses the USDA Food and Nutrient Database for Dietary Studies (FNDDS). The NDSR contains more than 11,100 food images and can handle the great majority of supermarket processed foods. It is adequate for characterizing intake for between-group comparisons, 3-day recalls will minimize intra-individual day-to-day variability and provide a better estimate of dietary intake. Energy and macronutrient content will be obtained from three NDSR dietary recalls by phone on randomly selected 2 weekdays and 1 weekend day, during the middle of each study period. 1-h recalls are less burdensome than food diaries and less likely to influence eating behavior, as it is without forewarning [151]. The NDSR is a fully computerized, interview-administered, validated, five-

	Protocol Name:	Multi-level supermarket discounts of fruits and vegetables on intake and health
	Principal Investigator:	[name]
	Primary Contact Name/Contact Info:	[name] [contact] [name] [contact]
	Date Revised:	8/7/20
	Study Number:	HS#: 16-00407 GCO#: 16-1050

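### As written, the covariate sensitivity analysis is almost bound to agree with the main model, so agreement is little evidence about COVID, store or season; free baseline means also cost precision for recalled intake

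*SAP*

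**What the plan says.** The SAP's main model has group, time and their interaction as fixed effects, and "the participant as the random effect to obtain the within-person differences in response to the intervention". Effects are DiD contrasts from baseline to 16 and 32 weeks of intervention and to 16 weeks after it. The SAP gives a reason for leaving covariates out: "No covariates were added to the main model because there were no baseline differences in covariates between discount groups". It then adds: "A sensitivity analysis was also performed on the ITT sample by adding key covariates to the model". The covariates are sex, age and season at enrolment, primary supermarket, COVID presence and income relative to the NYC median. No covariate-by-time term is mentioned.

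COVID is coded per participant: "The presence of COVID was assigned if the COVID-19 pandemic and lockdown period occurred during the intervention between 2/20/20 and 4/6/2021", and "The absence of COVID-19 was assigned if the COVID-19 pandemic period happened prior to or after the intervention". The SAP assumes data are missing at random. It mentions neither equal baseline means nor adjustment for baseline.

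In the Protocol (Study visit 2; wk 8), participants learn at week 8 that "they will be informed of their randomization into 1 of 3 discount level groups, stratified by gender within each grocery store". Under Measures, the dietary recalls are taken "on randomly selected 2 weekdays and 1 weekend day, during the middle of each study period".

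**The concern.** The main model has no covariates, so the sensitivity analysis is the only stated analysis that uses COVID, store or season. A reader will naturally take its agreement with the main model as reassurance on those factors. If the added terms cannot move the DiD, that reassurance is empty: the two models agree whether or not the pandemic, a store or the season altered change from baseline.

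Two related matters bear on the same model. The COVID flag may be too coarse to represent a pandemic effect on change, even if crossed with time. Estimating each arm's baseline mean freely also gives up precision that randomisation makes available. What is at stake is chance imbalance, precision and how the check is read.

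**Working it through.** The documents give no SD, correlation or enrolment dates for these analyses, so there is no stated figure to reproduce. The inputs taken from them are the model and window dates (SAP), the visit weeks 8, 24, 40 and 56, and 360 enrolled with 37.5% dropout, 360 × 0.625 = 225 (Protocol, Number of Subjects). I read the participant random effect as a random intercept.

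**1. Cancellation.** Write Y_it = group-by-time mean + b·x_i + u_i + e_it. The change from baseline is Y_it − Y_i0 = change in the group-by-time mean + e_it − e_i0. Both b·x_i and u_i drop out. With complete data the DiD is the same with or without x_i. With dropout, a little between-person information enters and leaves a small residual.

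Simulations used 360 people, three arms and random-intercept fits, with dropout missing at random. Shift from the main DiD to the covariate-adjusted DiD:

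- Complete data: zero to rounding.
- Within-person correlation (rho) about 0.4: mean 0.02 to 0.04 SE. The largest single-trial shift was 0.12 to 0.21 SE across separate runs, and 0.27 SE when dropout depended strongly on the covariates and differed by arm.
- rho 0.9: mean about 0.01 SE.

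A stress test planted a COVID effect on change of −0.8 SD with a 30-point imbalance between arms (rho 0.5, true DiD 75 g). The main model gave 19.0 g, the covariate main-effects model 18.7 g and covariate-by-time terms 77.4 g. This shows only that the check cannot see such an effect. The imbalance is not realistic: with 120 per arm its SE is at most √(2 × 0.25/120) = 6.5 points, so 30 points is about 4.6 SE.

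**2. The COVID flag.** Let s be the intervention start (week 8) in days from 2/20/20. The window runs from day 0 to day 411 and the intervention lasts 32 × 7 = 224 days. A person is flagged if s lies between −224 and 411, which is 636 start dates. Taking them as equally likely (an assumption), between week 8 and week 40:

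| Position | s | Dates | Share |
|---|---|---|---|
| Enters the window | −224 to −1 | 224 | 35% |
| Inside at both | 0 to 187 | 188 | 30% |
| Leaves the window | 188 to 411 | 224 | 35% |

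Over visits at s, s+112, s+224 and s+336, 412 + 412 + 412 + 300 = 1,536 of 4 × 636 = 2,544 fall inside, so 40% fall outside. As an arbitrary example, week 0 on 8/7/20 puts week 8 on 10/2/20 (inside) and week 40 on 5/14/21 (outside), yet the person counts as exposed. For recalls at assumed weeks 4 and 32, the shares are 31% entering, 26% leaving, 34% inside at both and 9% at neither.

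If COVID acts as an on/off shift, entering and leaving change the outcome in opposite directions, so flag-by-time averages them away. As an illustration, take an on/off effect of 0.5 SD at rho 0.4 with even start dates. The mean distance from the COVID-free DiD is 0.20 SE for the main model, the SAP sensitivity model and flag-by-time alike, and 0.03 SE with a visit-level in-window indicator. If the effect accumulates and persists (rho 0.9), the figures are 0.18 (main), 0.18 (SAP sensitivity), 0.12 (flag-by-time), 0.18 (indicator) and 0.03 SE (cumulative time in the window). The useful term depends on a form nobody knows.

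**3. Free baseline means.** Per arm of size n with equal variances, the change score has variance 2σ²(1−rho)/n. With equal or adjusted baselines it is σ²(1−rho²)/n. The ratio is 2/(1+rho).

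| Assumed rho | Ratio | Extra variance |
|---|---|---|
| 0.3 | 1.54 | 54% |
| 0.4 | 1.43 | 43% |
| 0.5 | 1.33 | 33% |
| 0.6 | 1.25 | 25% |
| 0.9 | 1.05 | 5% |
| 0.95 | 1.03 | 3% |

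With dropout at rho 0.4, simulation gives 36 to 37%. Where the equal-baseline model has 80% power, the free-baseline DiD has 62% at rho 0.3 and 71% at rho 0.6.

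**The case against.** The strongest reply has five parts.

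- **The SAP does not claim robustness.** It says covariates were added, not what agreement would prove. This stands: the warning concerns how the result may be read.
- **The specification is inferred from silence.** A one-paragraph SAP neither states nor excludes covariate-by-time terms. This also stands, and one sentence from the sponsor would settle the first part.
- **The check is not literally empty.** Dropout leaves single-trial shifts of up to 0.27 SE, and covariates can support the missing-at-random assumption and alter the reported estimated means. True, but the average shift is a few hundredths of an SE.
- **A reader might infer that COVID biased the primary DiD.** The documents do not support that. Randomisation within sex and store protects the DiD on average, and the distances above are chance imbalance that the SE largely covers. With no true discount effect, an on/off COVID effect of 0.5 SD and complete data, the main model's type I error at weeks 24, 40 and 56 was 4.4%, 6.0% and 5.2% at rho 0.4. At rho 0.9 it was 3.9%, 5.9% and 7.9%, but that correlation stands for weight, where an on/off effect is the less plausible form.
- **Equal baseline means are an efficiency option.** Correct: free means are valid, and the loss is in precision only.

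**Conclusion.** The point holds as a matter of interpretation and precision. Unless covariates were crossed with time, agreement between the two models is nearly automatic and is almost no evidence about COVID, store or season effects on change. The cancellation follows from the stated model. The residual of 0.01 to 0.04 SE on average rests on the assumed dropout mechanisms and correlations.

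It would be tempting to conclude that crossing the SAP's COVID flag with time cures the problem. It does not for an on/off effect, and no single replacement is known to be right.

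The precision loss is material for recalled intake if rho is about 0.3 to 0.6, which is plausible for three recalls per period but not stated. It is small for weight. The COVID and store magnitudes depend on assumed enrolment dates, number of stores, correlation and effect form, and are illustrations only. This is an improvement worth making, not a defect that overturns the primary analysis.

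**What to change.** Keep the stated results. Because the SAP is written in the past tense, label everything added as post hoc:

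- **(a)** State whether covariates were crossed with time. If not, report a model crossing at least the randomisation strata, sex and store, with time, pooling small stores.
- **(b)** Report a model with group means constrained equal at the pre-discount baseline.
- **(c)** As an exploratory check only, replace the per-person flag with a visit-level COVID term built from actual measurement dates. Say that the right form, in-window or cumulative, is unknown.
- **(d)** Do not cite agreement of the main-effects model as robustness to COVID, store or season.

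The cost is low, because measurement dates and strata should already be on file. With four stores (assumed; the Protocol says only several), sex and store by time add (1 + 3) × 3 = 12 parameters. In simulation with no COVID or store effect on change, these terms plus two visit-level COVID terms raised the SE by about 0.3% and moved the DiD by 0.06 SE on average through noise. Adding (b) left the SE about 14% lower at rho 0.4 and 2% lower at rho 0.9, with type I error of 4.6 to 5.1%. If stores have different trends (SD 0.25, assumed), crossing strata with time cuts the distance from 0.08 to 0.05 SE at rho 0.4 and from 0.17 to 0.04 SE at rho 0.9. The remaining downside is more analyst choice in a completed analysis, which the post hoc label should make plain.
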